1.1 Background and Rationale

TheraSphere[®], a localized, minimally embolic therapy, capitalizes on the hypervascularity nature of tumors delivering Yttrium-90 microspheres, a source of beta energy, via the hepatic artery to the tumor bed. The distribution of blood flow is 3 to 7 times greater within the tumor than the surrounding noncancerous tissue. Consequently, there is preferential delivery of microspheres to the tumor capillary bed allowing for higher doses of radiation to be delivered to the tumor relative to the surrounding non-tumor parenchyma. The ability to concentrate radioactive microspheres within the tumor leads to an "inside-out" radiation, which in turn exerts a local tumoricidal effect.

Preliminary data: Treatment details were retrospectively collected for a cohort of patients with advanced multifocal HCC at MD Anderson Cancer Center between January 2008 & May 2010 who received systemic sorafenib followed by liver directed therapy with Yttrium-90 microspheres. 19 patients met the criteria (BCLC stage B=3 patients, and BCLC stage C=16 patients), (Child-Pugh A=16, and Child-Pugh B=3). Response rate was: PR 21% (n=4) and 79% (n=15) of these patients had SD by RECIST criteria. Median TTP per liver tumors was 7.3 months, and OS was 10.3 months. Grade 3 /4 hepatic toxicities were absent within 30 days post Y90 microsphere therapy. Significant adverse events were: GI ulcer (1), pancreatitis (1), lymphopenia (1), and mucositis (2) from which all patients recovered uneventfully.

It will be also important in the future to determine how to most effectively integrate molecular assays that assess the likelihood of therapeutic benefit into clinical practice. Therefore, we plan to assess potential biological markers candidates to help predict response or survival benefit to this approach. Insulin like growth factor-1 (IGF-1) is produced predominantly in the liver, and our recent study showed that pre-treatment plasma IGF-1 may correlate with patients' survival, and hence improve the prognostic ability of the Cancer of the Liver Italian Program (CLIP) score, and Barcelona Clinic Liver Cancer (BCLC) staging. IGF-1 significantly correlated with the clinicopathologic features. With an optimal IGF-1 cut point of 26 ng/mL, the overall survival for patients with IGF-1 >26 was 17.7 months (95% CI of 13.6, 22.8), and for IGF-1 ≤ 26 (60/288 patients) was 5.8 months (95% CI of 4.0, 12.5), p-value<0.0001.

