Although sorafenib is a standard-of-care in the treatment of patients with HCC, it is associated with only a modest improvement in median survival as compared to best

supportive care. Further, sorafenib treatment is associated with significant toxicity. The most common adverse reactions (≥ 20 percent) considered related to sorafenib were fatigue, weight loss, rash/ desquamation, hand-foot skin reaction, alopecia, diarrhea, anorexia, nausea and abdominal pain. [2] Diarrhea was reported in 55 percent of sorafenib patients (grade 3 in 10 %). Hand-foot syndrome (21 percent overall; grade 3 in 8 %) and rash (19 % overall; grade 3 in 1 %) were the most common dermatologic adverse reactions to sorafenib. Sorafenib dose reductions and drug holidays are often required to manage these toxicities.

Adhoc subset analysis of the SHARP trial data indicated that the efficacy of sorafenib is reduced in an important subset of patients with advanced HCC. [8] In patients with extrahepatic spread or macroscopic vascular invasion, the median survival was 8.9 months in patients treated with sorafenib as compared to 6.7 months in patients treated with placebo.

The long-term experience of TheraSphere in the treatment in 291 patients with HCC as part of a single-center, prospective, longitudinal cohort study were recently reported. [9] A total of 526 treatments were administered (mean, 1.8; range, 1-5). Toxicities included fatigue (57%), pain (23%), and nausea/vomiting (20%); 19% exhibited grade 3/4 bilirubin toxicity. The 30-day mortality rate was 3%. Response rates were 42% and 57% based on WHO and EASL criteria, respectively. The overall TTP was 7.9 months (95% confidence interval, 6-10.3). Survival times differed between patients with Child-Pugh A and B disease (A, 17.2 months; B, 7.7 months; $P = .002$). Patients with Child-Pugh B disease who had portal vein thrombosis (PVT) survived 5.6 months (95% confidence interval, 4.5-6.7). Baseline age; gender; performance status; presence of portal hypertension; tumor distribution; levels of bilirubin, albumin, and alpha-fetoprotein; and WHO/EASL response rate predicted survival. These investigators concluded that patients with Child-Pugh A disease, with or without PVT, benefited most from treatment. Patients with Child-Pugh B disease who had PVT had poor outcomes. Therefore, TTP and overall survival varied by patient stage at baseline.

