Results from a separate cohort of 108 consecutive patients with advanced HCC using TheraSphere demonstrated a median overall survival from treatment of 16.4 months, with median time to progression of 10.0 months. [10] Tumor response at 90 days evaluated by RECIST in 62 patients were complete or partial response 10 (16%), stable disease 46 (74%) and progressive disease 6 (10%). Toxicities were generally mild to moderate. The most common being transient fatigue during the week following administration (61%) and abdominal pain (56%). For patients with normal bilirubin at enrollment, 32% experienced Grade 1 or 2 elevations and three patients developed Grade 3 elevations. For patients with elevated bilirubin at enrollment, 17% experienced Grade 2 elevations and 30% experienced Grade 3 or 4 elevations. In the majority of patients, bilirubin returned to baseline values within 4-6 weeks. The conclusion was that Therasphere is safe and effective, even in patients with compromised liver function.

Preliminary results of a Phase II investigation of the safety, tolerability and efficacy of administering TheraSphere and Nexavar (sorafenib) treatment in 26 patients with HCC indicate that the combination is safe. [11] In this trial, all patients began sorafenib 400 mg BID at least 7 weeks in advance of TheraSphere treatment. Most patients (65%) required sorafenib dosage adjustment. The most common toxicities were diarrhea, fatigue and hand foot syndrome with most being self-limiting and responsive to sorafenib dose adjustment.

One single grade 4 toxicity of worsening cirrhosis was observed. Median survival is 15.5 months which exceeds that reported in the sorafenib or placebo arms of the SHARP study (10.7 and 7.9 months respectively). The reported toxicities are consistent with the toxicity profile of both TheraSphere and sorafenib with no apparent increase in severity or frequency.

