8.1 Statistical and analytical plans

Statistical consideration for 2012-0870: study of sorafenib plus theraspheres for extrahepatic hepatocellular carcinoma (redesign, 20 patients have enrolled in study 2012-0870)

This is a phase II study of sorafenib plus theraspheres for extrahepatic hepatocellular carcinoma (EHC). The primary objective is to evaluate the progression-free survival (PFS), where the progression-free survival will be measured from the start of therapy until failure to disease progression or death.

Historical data showed that the median PFS was 4.1 months for EHC patients treated with sorafenib alone. We expect that the combination treatment would improve the PFS. A maximum of 40 will be recruited for the study at a rate of 1-2 patients per month. The study will monitor toxicity and futility.

Futility monitoring

The primary endpoint PFS will be monitored using the method of Thall et al. (2005), and we will stop enrolling patients to the study if, based on the available data, we have little reason to believe that the median PFS of the combination therapy (m_E) is more than that of sorafenib alone (m_S) in the historical data, which was 4.1 months. Formally, we'll stop the study early if

$$\text{Prob}(m_E > m_S | \text{data}) < 0.15$$

That is, if there is less than 15% chance the median PFS of the combination therapy is more than that of sorafenib, the trial will be stopped. Where m_S represents the median PFS for sorafenib alone in the historical data with an inverse gamma distribution $IG(11, 41)$, which corresponds to a mean of 4.1 months and a variance of 1.87. m_E represents the median PFS for the study combination therapy, assuming the prior for m_E is $IG(2.17, 4.8)$, which has the same mean as m_S but with a much larger variance (i.e. 99) to reflect much greater uncertainty about the median PFS of the combination therapy of sorafenib and theraspheres.

Futility monitoring will start once 20 patients have been enrolled. Assuming an accrual rate of 1.5 per month and an additional follow-up of 12 months, the operating characteristics for the futility stopping rule under various true states are summarized in the following table 8, with results based on 5000 simulations.

Table 8. Operating characteristics for the time-to-progression monitoring

True Median Time to progression	Pr(stop early)	Average Number of Patients Treated (25th, 75th percentiles)
2	0.993	21 (20, 20)
3	0.529	31.4 (20, 40)
4	0.100	38.3 (40, 40)

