The Department of Biostatistics will provide and maintain a website (“Clinical Trial Conduct”: <https://biostatistics.mdanderson.org/ClinicalTrialConduct/>) for futility monitoring for each treatment arm on this study. The Clinical Trial Conduct website resides on a secure server, and access is gained through usernames and passwords provided to personnel responsible for enrolling patients and updating patient data. The website is accessed through a browser using secure socket layer (SSL) technology. Personnel responsible for enrolling patients on trials, which includes the principal investigator(s), research nurse(s), and data coordinator(s), will be trained by members of the Department of Biostatistics in the use of the trial website; the importance of timely updating of follow-up times and recording of events will be emphasized in training.

Analysis Plan:

Primary analysis

Once the trial is completed, the posterior median time to progression and its 95% credible interval will be estimated. In addition, posterior probability that the median PFS is more than

sorafenib will be assessed. Furthermore, Kaplan-Meier method will be used to estimate median PFS and the 95% confidence interval. Log rank test, univariate and multivariate Cox proportional hazards regression models will be used to identify prognostic factors for PFS.

Secondary analysis

Toxicity rate and mortality rate will be estimated with a 90% credible interval. the posterior probability that the toxicity rate is greater 30% will be evaluated as well. Binary endpoints such as response will be tabulated by frequency and the corresponding 95% confidence interval (CI). Fisher's exact test will be applied to compare the patient characteristics between responders and non-responders. Univariate and multivariate logistic regression models will be fit to identify clinical factors associated with overall response. The time-to-event endpoints will be analyzed using Kaplan-Meier method, Log rank test and Cox proportional hazards regression modeling. Discrete or categorical patient-reported outcomes and quality of life assessments will be tabulated by frequency and 95% CI, while for the continuous data, summary statistics including n, mean, and standard deviation, median, minimum and maximum will be computed.

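### Ordinary multivariable logistic regression for response would rest on about 6 to 8 responders; use a penalised or exact method with at most one or two pre-named factors

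*Combined protocol and SAP*

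**What the plan says.** Section 8.1 (Analysis Plan, Secondary analysis) commits to this for response: "Univariate and multivariate logistic regression models will be fit to identify clinical factors associated with overall response". The same paragraph plans a table of response with a 95% confidence interval, and Fisher's exact test of patient characteristics between responders and non-responders. It does not list the factors or cap their number. It gives no expected number of responders, no penalised or exact estimator, and no fallback if the model does not converge.

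The size is set in the same section: "A maximum of 40 will be recruited for the study at a rate of 1-2 patients per month". Futility monitoring starts at 20 patients, so the trial can end there.

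Lesions are assessed by RECIST 1.1 (synopsis, Imaging Requirements). The documents quote RECIST response in two cohorts:
- Section 1.1, the retrospective cohort on the same combination: "Response rate was: PR 21% (n=4) and 79% (n=15) of these patients had SD by RECIST criteria".
- Section 2.3, the TheraSphere cohort of 108: 10 complete or partial responses among 62 evaluated patients (16%).

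Section 2.3 also quotes a 291-patient TheraSphere cohort under other criteria: "Response rates were 42% and 57% based on WHO and EASL criteria, respectively".

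**The concern.** The precision of a logistic model is governed by the smaller outcome group, not by the number of patients. With 6 to 8 responders, a binary factor can easily have no responders, or only responders, at one of its levels. The data are then separated: the maximum-likelihood odds ratio is infinite and the software reports non-convergence or an arbitrary large value. Where the fit does converge, the estimate is poorly determined and tends to lie too far from 1.

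At stake is the usefulness of one exploratory secondary analysis. As written, it may return no estimate, or one whose size cannot be relied on, and the plan does not say what the analyst should then do.

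**Working it through.** **1. The plan's own rates.** 4/19 = 21.1%, 15/19 = 78.9% and 10/62 = 16.1%. All agree with the text.

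**2. Expected responders = N × rate.**

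| Rate | N = 40 | N = 20 |
|---|---|---|
| 10/62 | 40 × 0.161 = 6.5 | 20 × 0.161 = 3.2 |
| 4/19 | 40 × 0.211 = 8.4 | 20 × 0.211 = 4.2 |

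At N = 40 the central 95% binomial ranges are 2 to 11 and 4 to 14 responders. The probability of fewer than 10 responders is 0.90 at 16% and 0.68 at 21%. With three factors there are 6.5/3 = 2.2 to 8.4/3 = 2.8 responders per factor; with five, 6.5/5 = 1.3 to 8.4/5 = 1.7. Stopping early is a realistic prospect: Table 8 gives it probability 0.529 if the true median is 3 months and 0.100 if it is 4.

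**3. How often maximum likelihood fails.** Datasets were simulated with N = 40 and no true effects. The number and type of covariates are assumptions, because the plan gives none. Entries are the percentage of trials with separation or non-convergence; each range runs from the 21% to the 16% response rate.

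| Assumed covariates | 3 factors | 5 factors |
|---|---|---|
| All binary, prevalence 20–50% | 24–39% | 39–51% |
| Binary (20–50%) and continuous, alternating | 21–30% | 28–42% |
| A further mixed set | 8–19% | 17–28% |
| Balanced binary and continuous | 4–11% | 6–17% |
| All continuous | 0.3–0.5% | 0.3–3.3% |

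The first, second and last rows used 800 datasets per cell and the balanced row 3,000. With two binary factors the failure rate is 10–21%. At N = 20, a 21% rate and three binary factors, it is 67%.

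**4. Imprecision.** The percentage of trials in which the fit fails or gives at least one odds ratio above 5 or below 1/5 is:
- all binary: 42–54% (3 factors), 61–75% (5);
- alternating mixed: 34–43% (3), 49–64% (5);
- all continuous, per standard deviation: 3–9% (3), 9–19% (5).

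Among converged mixed models, a binary factor with true odds ratio 1 is estimated above 3 or below 1/3 in about 21–36% of fits. A one-factor model does so in about 20%.

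**5. False positives.** In converged null fits, a given binary factor reached Wald p < 0.05 in about 1–4%, which is below nominal. At least one factor did so in 5–9% of trials with three covariates and 9–16% with five. For comparison, independent tests at 5% would give 1 − 0.95³ = 14% and 1 − 0.95⁵ = 23%.

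**6. The alternative estimator.** Firth-penalised estimation gave finite estimates in practically every such dataset.

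**The case against.** Four points on the other side have force.

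**The failure rate is not a property of the plan.** It depends on the covariates, and the plan names none. A reader might infer that the model will usually break down. The documents do not support that: with one or two factors, or only continuous ones, failure is much less frequent. What stands is that nothing in the plan confines the model to those cases.

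**The analysis does not manufacture significant noise.** A reader might infer that it will falsely identify clinical factors. Step 5 shows otherwise: error per factor is below nominal, and the chance of any significant factor is no worse than ordinary multiplicity. Non-convergence is also visible to the analyst. Much of the imprecision comes from having few responders, since a one-factor model already gives a more than threefold odds ratio in about 20% of fits. Dropping the multivariable model would not cure that.

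**Higher response rates are quoted too.** At 42% and 57% the smaller outcome group among 40 would be 40 × 0.42 = 16.8 responders or 40 × 0.43 = 17.2 non-responders. With three binary factors at 42%, separation falls to 3%. Those rates use WHO and EASL criteria in another cohort, however, whereas this trial uses RECIST 1.1. The count of 6 to 8 therefore stands, as a statement about the RECIST rates.

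**The same criticism does not carry over to PFS.** Section 8.1 also says "univariate and multivariate Cox proportional hazards regression models will be used to identify prognostic factors for PFS". A reader might take the 25 events in that section as the information available and infer a limit of two or three covariates. But the 25 events only illustrate a credible interval, and such a limit is a rule of thumb. At 1.5 patients per month (40/1.5 = 26.7 months of accrual) plus 12 months, with exponential PFS of median 4.1 months (hazard ln 2/4.1 = 0.169), the mean proportion still event-free is (e^(−0.169×12) − e^(−0.169×38.7))/(0.169×26.7) = 0.029. That leaves about 39 events among 40 before dropout.

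Finally, response is not among the objectives in Section 3, and the IGF-1 objective there is tied to TTP and OS. No stopping rule depends on the response model.

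**Conclusion.** The point holds in a limited form. At the documents' RECIST rates, the planned response model would have about 6 to 8 responders at full accrual and 3 to 4 at 20 patients. With 3 to 5 covariates that include binary ones, ordinary maximum likelihood fails in roughly 4% to 50% of null trials (about 8% to 28% in one mixed set). Estimates that are obtained are very imprecise and tend to be too far from 1.

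This rests on three assumptions: response near 16% to 21%, evaluable in all patients; unpenalised maximum likelihood, since no other estimator is named; and a covariate set that the plan leaves open. The weakness concerns estimation and pre-specification, not error control, and leaves the primary PFS conclusion and the monitoring rules untouched. It is a minor, inexpensive improvement to an exploratory analysis.

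**What to change.** In Section 8.1, Secondary analysis:
- Replace ordinary maximum-likelihood logistic regression for response with Firth-penalised or exact logistic regression, reporting odds ratios with confidence intervals.
- Drop the multivariable response model, or restrict it to at most one or two factors named before the analysis.
- Label these analyses exploratory, alongside the Fisher's exact tests already planned.

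The cost is a change of SAP wording. Both methods are standard procedures in SAS, which the synopsis already names, and no new data, patients or visits are needed. The downside is little or no covariate adjustment for response. Penalisation gives finite, less extreme estimates but adds no information, so the intervals will remain wide and should be reported as such.

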8.2 Planned interim analyses

None

8.3 Determination of sample size

Please see 8.1

9. Data handling and quality assurance

9.1 Archiving

Essential documents shall be archived safely and securely in such a way that ensures that they are readily available upon authorities' request.

Patient (hospital) files will be archived according to local regulations and in accordance with the maximum period of time permitted by the institution.

10. Premature termination of the study

- If risk-benefit ratio becomes unacceptable owing to, for example,
 - Safety findings from this study (e.g. SAEs)
 - Results of any interim analysis
 - Results of parallel clinical studies
 - Results of parallel animal studies
(on e.g. toxicity, teratogenicity, carcinogenicity or reproduction toxicity).

- If the study conduct (e.g. recruitment rate; drop-out rate; data quality; protocol compliance) does not suggest a proper completion of the trial within a reasonable time frame.

11. Ethical and legal aspects

11.1 Ethical and legal conduct of the study

The procedures set out in this protocol, pertaining to the conduct, evaluation, and documentation of this study, are designed to ensure that the investigator abide by Good Clinical Practice (GCP) guidelines and under the guiding principles detailed in the Declaration of Helsinki. The study will also be carried out in keeping with applicable local law(s) and regulation(s).

Documented approval from appropriate IEC(s)/IRBs will be obtained for all participating centers before start of the study, according to GCP, local laws, regulations and organizations. When necessary, an extension, amendment or renewal of the EC/IRB approval must be obtained and also forwarded to Bayer.

Strict adherence to all specifications laid down in this protocol is required for all aspects of study conduct; the investigator may not modify or alter the procedures described in this protocol.

Modifications to the study protocol will not be implemented by the investigator without discussion and agreement by Bayer. However, the investigator may implement a deviation from, or a change of, the protocol to eliminate an immediate hazard(s) to the trial subjects without prior IEC/IRB/Bayer approval/favorable opinion. As soon as possible, the implemented deviation or change, the reasons for it and if appropriate the proposed protocol amendment should be submitted to the IEC/IRB/head of medical institution. Any deviations from the protocol must be explained and documented by the investigator.

The Principal Investigator is responsible for the conduct of the clinical trial at the site in accordance with Title 21 of the Code of Federal Regulations and/or the Declaration of Helsinki. The Principal Investigator is responsible for personally overseeing the treatment of all study patients. The Principal Investigator must assure that all study site personnel, including sub-investigators and other study staff members, adhere to the study protocol and all FDA/GCP/NCI regulations and guidelines regarding clinical trials both during and after study completion.

The Principal Investigator at each institution or site will be responsible for assuring that all the required data will be collected and properly documented.

11.2 Subject information and consent

Each subject / legal representative or proxy consentor will have ample time and opportunity to ask questions and will be informed about the right to withdraw from the study at any time without any disadvantage and without having to provide reasons for this decision.

Only if the subject / legal representative or proxy consentor voluntarily agrees to sign the informed consent form and has done so, may he/she enter the study. Additionally, the

investigator and other information provider (if any) will personally sign and date the form. The subject / legal representative or proxy consentor will receive a copy of the signed and dated form.

The signed informed consent statement is to remain in the investigator site file or, if locally required, in the patient's note/file of the medical institution.

In the event that informed consent is obtained on the date that baseline study procedures are performed, the study record or subject's clinical record must clearly show that informed consent was obtained prior to these procedures.

1. If the patient is not capable of providing a signature, a verbal statement of consent can also be given in the presence of an impartial witness (independent of Bayer and the investigator). This is to be documented by a signature from the informing physician as well as by a signature from the witness.
2. For minors or adults under legal protection, consent shall be given by the legal guardian(s). The consent of a minor or adult under legal protection shall also be requested where such a person is able to express his/her own will. His/her refusal or the withdrawal of his/her consent may not be disregarded.
3. In emergency situations, when prior consent of the patient is not possible, the consent of the patient's legal representative(s) or proxy consentor, if present, should be requested. The patient should be informed about the study as soon as possible and his/her consent to continue the study should be requested.

The informed consent form and any other written information provided to subjects / legal representatives or proxy consentors will be revised whenever important new information becomes available that may be relevant to the subject's consent, or there is an amendment to the protocol that necessitates a change to the content of the subject information and / or the written informed consent form. The investigator will inform the subject / legal representative or proxy consentor of changes in a timely manner and will ask the subject to confirm his/her participation in the study by signing the revised informed consent form. Any revised written informed consent form and written information must receive the IEC/IRB's approval / favorable opinion in advance of use.

